9.2. Sample Size Determination

The total study sample size is 450 participants with a 2:2:2:2:1:1 randomization ratio, where 90 participants will be randomly allocated to each of the arms including a JNJ-3989 dose (Arms 1 to 4) and 45 participants will be randomly assigned to each of the arms with no JNJ-3989 component (Arms 5 and 6).

Statistical power to test a dose-response signal was assessed using the generalized version of the MCP-Mod approach²⁸ applied to the binary primary efficacy endpoint on the logit scale for Arms 2, 3 and 4 (JNJ-3989 at 200, 100, and 40 mg dose, respectively +NA), and Arm 6 (Placebo+Placebo+NA) as control.

Five different assumptions were made for the dose-response relationship on the logit scale (see Figure 2) over the 3 doses of JNJ-3989 (40 mg, 100 mg and 200 mg) +NA.

[figure not shown]

Figure 2: Candidate Dose-response Models on the Logit Scale

Assuming a response rate for the highest dose of JNJ-3989 of at least 25%, and a one-sided alpha level of 5%, the power to conclude a positive dose-response trend over the 3 JNJ-3989 doses on the background of NA is \geq 85% under all candidate models (see Table 6).

Table 6:	Power to Conclude a Positive Dose-response Under the Assumed Candidate Dose-response
	Models

Response Rate	E_{max}	E_{max}	Linear	$SigE_{max}$	Exponential
for the	$(ED_{50}=5 \text{ mg})$	$(ED_{50}=100 \text{ mg})$		$(ED_{50}=110 \text{ mg}, h=8.0)$	$(\delta = 40)$
Highest					
JNJ-3989					
Dose					
20%	0.582	0.794	0.877	0.930	0.949
25%	0.851	0.953	0.978	0.991	0.994
30%	0.956	0.992	0.999	0.999	1.000

ED₅₀: dose that produces half of E_{max}; E_{max}: maximum effect; SigE_{max}: sigmoid E_{max}

The operational characteristics of the sequential testing approach as described in Section 9.1 are summarized in Table 7 for a variety of scenarios. In all scenarios, the primary endpoint response rate of the JNJ-3989 100 mg +NA arm is set between 25% and 35% whereas the rate of JNJ-6379+NA and the combination regimen JNJ-3989 100-mg dose+JNJ-6379+NA vary. Under these scenarios, the probability to find a significant signal (max trend test for positive dose-response) is ≥87% for an absolute response rate in the 100 mg dose of JNJ-3989 (Arm 3) of at least 25 %.

Simulations were conducted using the normal approximation test for the difference in binomial proportions to determine the power level in the comparison of the primary efficacy endpoint among the combination regimens at one-sided alpha of 0.05.

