1.4. Sample Size Justification

The total study sample size is 450 participants with a 2:2:2:2:1:1 randomization ratio, where 90 participants will be randomly allocated to each of the arms including a JNJ-3989 dose (Arms 1 to 4) and 45 participants will be randomly assigned to each of the arms with no JNJ-3989 component (Arms 5 and 6). Due to the global impact of the pandemic Coronavirus Disease 2019 (COVID-19) and the use of the modified ITT analysis set as primary set for the efficacy analyses, study enrollment was extended by approximately 5% of participants.

Statistical power to test a dose-response signal (max trend test) was assessed using the generalized version of the MCP-Mod ([Pinheiro J. et al., 2014](#)) applied to the binary primary efficacy endpoint on the logit scale using data from Arms 2, 3, and 4 (JNJ-3989 at 200, 100, and 40 mg dose, respectively +NA), and Arm 6 (placebo+placebo+NA) as control. The “max trend test” is to test the null hypothesis that none of the doses is better than control (i.e. the flat dose response curve). The power to reject the null hypothesis is $\geq 85\%$ under all 5 candidate dose-response models for an absolute response rate of the highest dose of JNJ-3989 of at least 25% (one-sided alpha level of 5%). In addition, assuming a response rate of 5% in control Arm 6, the study sample size provides a statistical power $\geq 84\%$ to detect a difference of $\geq 20\%$ in the primary endpoint between Arm 1 and Arm 6, and power $\geq 76\%$ for at least a 20% delta between Arm 5 and Arm 6, using a fixed sequence approach for controlling for multiplicity.

The testing among the regimens (Arm 1, 3, and 5) will be performed using the min test approach control for the one-sided Type 1 error of 0.05. The chosen study sample size and randomization allocation provides acceptable power levels also for the comparison of different combination regimens, ie, JNJ-3989+JNJ-6379+NA (Arm 1, 100-mg dose of JNJ-3989) versus JNJ-3989+NA (Arm 3, 100-mg dose of JNJ-3989), and versus JNJ-6379+NA (Arm 5), respectively. For example, for the same delta of 25% between Arm 1 and Arm 3 and between Arm 1 and Arm 5, the power to conclude that Arm 1 is statistically superior to Arm 3 and Arm 5 is 87%, assuming a response rate of 25% in both Arm 3 and 5. Details are provided in Section 9 of the protocol Amendment 1.

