5.1.1. Level of Significance

The study addresses two separate research questions:

- 1) Dose finding: the comparisons of 3 doses of JNJ-3989+NA (Arms 2, 3, and 4) against NA treatment alone (Arm 6) and other comparisons of active regimens (Arm 1 and Arm 5) vs Arm 6,
- 2) Regimen finding: the comparisons of the combination regimen of JNJ-3989 (100 mg) +JNJ-6379 +NA (Arm 1) vs each of the mono components JNJ-3989 (100 mg) and JNJ-6379, respectively, on the background of NA (Arm 3 and Arm 5).

For the primary efficacy endpoint analysis, the Type 1 error rate is controlled at 0.05 one-sided level for multiple comparisons within each separate research question differently and independently.

For the comparisons against the control, a fixed sequence approach is used where the first step implements the multiple contrast test of the MCP-Mod methodology (applied to Arms 2, 3, 4, and 6) to detect a trend test among the JNJ-3989 doses (40 mg, 100 mg and 200 mg), under the null hypothesis of no differences across the four arms, which is followed by the pairwise comparison of Arm 1 vs Arm 6, followed by the pairwise comparison of Arm 5 vs Arm 6. Based on the fixed sequence principle, each step must be found statistically significant at a one-sided 0.05 level in order to proceed to the next step.

For the comparisons among the regimens (Arms 1, 3, and 5), the min test principle is used. The JNJ-3989+JNJ-6379+NA combination regimen Arm 1 will be declared statistically superior to the dual regimens (Arm 3 and Arm 5) if both tests of Arm 1 vs Arm 3 and Arm 1 vs Arm 5 demonstrate statistical significance at the one-sided 0.05 level.

For the key secondary endpoint, the same multi-step testing strategy as the one implemented for the primary efficacy endpoint described above, using MCP-Mod and additional treatment arms pairwise comparisons against control in a fixed sequence, as well as the min test approach separately for between-regimen comparisons, will be used for this key secondary endpoint. However, the comparisons with NA control in the testing strategy applied to this efficacy endpoint will be made against the NA historical control benchmark of 5%, instead of the study NA control arm (Arm 6).

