After a positive significant dose-response signal is established for the combination regimen JNJ-3989+NA, the testing procedure continues in a fixed sequence to control the type 1 error in presence of multiple testing, with the comparison of Arm 1 (JNJ-3989+JNJ-6379+NA) with control Arm 6 at a one-sided alpha of 0.05. If Arm 1 is found statistically superior to control Arm 6, then the combination regimen JNJ-6379+NA (Arm 5) is compared to control Arm 6 at 0.05 one-sided alpha level. The Mantel-Haenszel (MH) test (Mantel N. et al., 1959) for the difference of 2 proportions adjusted for the 2 randomization stratification factors (treatment history

status and screening HBeAg status) will be used at one-sided 0.05 alpha level in each of the above mentioned pairwise comparisons.

5.2.2.1.1.3. Scientific Question Part c: Comparisons Among Combination Regimens

For the regimen-finding objective, the statistical comparisons among the regimens (Arm 1, 3, and 5) will be performed using the min test approach to control for the Type I error rate at the one-sided 0.05 alpha level. The JNJ-3989+JNJ-6379+NA combination regimen will be declared statistically superior to the dual regimens if both tests of Arm 1 vs Arm 3 and Arm 1 vs Arm 5 demonstrate statistical significance at the one-sided 0.05 level. The Mantel-Haenszel test for the difference of 2 proportions adjusted for the 2 randomization stratification factors will be applied.

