For Mod-step, model averaging techniques across all 5 candidate models will apply to each imputed dataset and produce the weighted estimates of the treatment effect across the JNJ-3989 dose range (0 mg to 200 mg). The standard errors will be obtained using bootstrapping techniques and then combined into one result using PROC MIANALYZE. The final response estimates on the logit scale for each dose level in the range 0 mg to 200 mg and their 90% CI will be back transformed to the original scale of proportion of responders and plotted with the corresponding 90% confidence band.

For pairwise comparisons of Arms 1 vs 6 and Arm 5 vs 6, as well as the comparisons amongst combination regimens (Arms 1, 3, and 5), the MH test will be performed for each dataset to generate individual estimates of the difference in proportions and the standard error adjusted on

stratification factors. Then the results from these multiple imputed datasets are combined (pooled) for obtaining the overall inference and p-value in a way that accounts for the variability between imputations (Ratitch B. et al., 2013)

Depending on the amount of missing data, the number of imputed datasets to be generated will be increased appropriately from the planned 200 to ensure robustness in the MI results and relative efficiency (Graham JW. et al., 2007).

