Therefore, within the MCP-Mod framework, the MCP analysis to test the null hypothesis that none of the 3 JNJ-3989 doses (40 mg, 100 mg, and 200 mg)+NA is better than historical control NA (i.e. the flat dose response curve) will assume:

- the point estimate for the response rate of the “JNJ-3989 dose=0 mg historical NA” is 0.05,
- the estimated variance, on the logit scale, of the point estimate for the response rate of the “JNJ-3989 dose=0 mg historical NA” historical group is 0.0275.

Characterization of the dose-response model: The model averaging techniques (Bornkamp B. et al., 2009) across the candidate models will be utilized to derive the dose-response shape and to evaluate the desired dose(s) of JNJ-3989 (modeling step). The estimated dose response curve and the corresponding confidence band will be plotted against the JNJ-3989 dose range of 0 mg to 200 mg.

5.3.2.1.1.2. Scientific Question Part b: Pairwise Comparisons vs Historical Control

For the pairwise comparison against the fixed historical control value of 5% for Arms 1 and Arm 5, respectively, the Clopper-Pearson test will be used at one-sided 0.05 alpha level, based on a fixed sequence testing approach as described in Section 5.1.1.

5.3.2.1.1.3. Scientific Question Part c: Comparisons Among Combination Regimens

For the regimen-finding objective, the testing among the regimens (Arm 1, 3, and 5) will be performed at a one-sided 0.025 alpha level using the min test approach to provide evidence of superior efficacy of the triple regimen Arm 1 over the dual regimens Arm 3 and Arm 5, for

regulatory consideration. This analysis is performed at a more stringent α -level because it aims to support the selection of the combination drug therapy to be studied in confirmatory studies. The JNJ-3989+JNJ-6379+NA combination regimen Arm 1 will be declared statistically superior to the dual regimens Arm 3 and Arm 5, if both tests of Arm 1 vs Arm 3 and Arm 1 vs Arm 5 demonstrate statistical significance at the one-sided 0.025 level. The Mantel-Haenszel test for the difference of 2 proportions adjusted for the 2 randomization stratification factors will be applied.

Further, the functional cure efficacy endpoint will be summarized for the control Arm 6 with the point estimate paired with its 90% CI using the Clopper-Pearson exact method to assess the consistency with the assumed historical control value of 5%.

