For the MCP-step, the max trend test will be obtained for each of the imputed datasets and the multiplicity adjusted p-value associated with the largest T-test statistic will be saved. All p-values will be transformed to a Z-test statistic using the inverse cumulative distribution function of the standard normal distribution. The resulting 200 Z-test statistics and their standard error of 1 will be combined into an overall Z test result, using SAS PROC MIANALYZE.

For Mod-step, model averaging techniques across all 5 candidate models will apply to each imputed dataset and produce the weighted estimates across all models of the treatment effect across the JNJ-3989 dose range (0 mg and 200 mg). The standard errors will be obtained using bootstrapping techniques and then combined into one result using PROC MIANALYZE. The final response estimates on the logit scale for each dose level in the range 0 mg to 200 mg and their 90% CI will be back transformed to the original scale of proportion of responders and plotted with the corresponding 90% confidence band.

For pairwise comparisons against the fixed historical control value of 5% for Arm 1 and Arm 5, the estimated proportion with the asymptotic standard error will be obtained for each dataset. Then the results from these multiple imputed datasets are combined (pooled) for obtaining the overall inference and p-value in a way that accounts for the variability between imputations ([Ratitch B. et al., 2013](#)). Depending on the amount of missing data, the number of imputed datasets to be generated will be increased appropriately to ensure robustness in the results ([Graham JW. et al., 2007](#)).

For comparisons amongst combination regimens (Arms 1, 3, and 5), the MH test will be performed for each dataset to generate individual estimates of the difference in proportions and the standard error adjusted on stratification factors. Then the results from these multiple imputed datasets are combined (pooled) for obtaining the overall inference and p-value in a way that accounts for the variability between imputations ([Ratitch B. et al., 2013](#)). Depending on the amount of missing data, the number of imputed datasets to be generated will be increased appropriately from the planned 200 to ensure robustness in the MI results.

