5.3.4.1. Main Estimator

To assess the functional cure rate against the observed proportion in the control Arm 6, for this estimator, the same statistical model (MCP-Mod, and stratum-adjusted MH test), data included, assumptions, and MI approach for handling missing data and approach to control the Type I error rate will be used as for the main estimator of the main estimand for the primary endpoint (Section [5.2.2.1](#)). The MCP-Mod approach and pairwise statistical tests to compare with control will be based on the data from Arm 6 instead of historical control fixed value of 5%. The MCP-step will use the actual data from Arm 6, and statistical test to compare Arm 1 and Arm 5 to control will be the MH test as it compares 2-sample proportions.

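### The SAP does not say which variance is pooled for the pairwise Mantel-Haenszel tests; with the usual risk-difference standard error, the two 90-vs-45 comparisons run at about 0.10–0.13 instead of 0.05 at response rates of 2–5%

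*SAP*

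**What the plan says.** SAP 5.2.2.1.1.2 sets the comparison of Arm 1 "with control Arm 6 at a one-sided alpha of 0.05", then Arm 5 with Arm 6, after the MCP-Mod step has succeeded. The test is the 1959 Mantel-Haenszel test for a difference of two proportions, adjusted for the two stratification factors.

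SAP 5.2.2.1.4 turns this into a calculation on the imputed data. For the two comparisons with Arm 6 and for those among the regimens, "the MH test will be performed for each dataset to generate individual estimates of the difference in proportions and the standard error"; the results are then pooled for the overall inference and p-value. SAP 5.3.2.1.4 does the same for functional cure: "For comparisons amongst combination regimens (Arms 1, 3, and 5), the MH test will be performed for each dataset". There the regimen claim is made "if both tests of Arm 1 vs Arm 3 and Arm 1 vs Arm 5 demonstrate statistical significance at the one-sided 0.025 level". In the supplementary estimand against Arm 6 (SAP 5.3.4.1), the "statistical test to compare Arm 1 and Arm 5 to control will be the MH test".

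SAP 5.1.1 states that "the Type 1 error rate is controlled at 0.05 one-sided level for multiple comparisons within each separate research question". Neither document gives a formula for the standard error that is pooled.

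**The concern.** An estimate and its standard error, pooled over imputations and divided, give a Wald-form test. The standard errors that normally accompany an MH risk difference (Sato, Greenland-Robins) are built from the observed arm proportions, not under the null. If the smaller arm has no responders, it adds nothing to the standard error. With 90 vs 45 participants and a low common response rate this happens often, and very few responders in the larger arm are then enough for significance. The statistic of the cited 1959 test does not behave this way.

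At stake are the first pairwise step of the fixed sequence (Arm 1 vs 6) and one of the two components of the regimen test (Arm 1 vs 5). The functional-cure version of the latter is set at 0.025 for regulatory use.

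**Working it through.** **Inputs.** Arms 1 and 3 have 90 participants each; Arms 5 and 6 have 45 each (SAP 1.4). One-sided alpha is 0.05, or 0.025 for the key secondary regimen test (SAP 5.1.1, 5.3.2.1.1.3). The assumed control rate is 5% (SAP 1.4). For strata, 40% are not currently treated, of whom 40% are HBeAg-positive (protocol 4.1), giving 16% and 24%. The split of the remaining 60% is not given; 15%/45% is assumed.

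**Formulas.** With d = p̂1 − p̂2:
- non-null: z = d / √[p̂1(1−p̂1)/n1 + p̂2(1−p̂2)/n2]
- null: z = d / √[p̄(1−p̄)(1/n1+1/n2)], where p̄ = (x1+x2)/(n1+n2)

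Type I error is the exact binomial probability, with the same rate in both arms, of all tables whose z exceeds the critical value.

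**The plan's own figures first.** Protocol 9.2 says "Simulations were conducted using the normal approximation test for the difference in binomial proportions to determine the power level". Its Table 7 gives min-test power of 0.871 at 50% vs 25% and 25%; enumeration with the null variance also gives 0.871. For Arm 1 vs 5:

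| Arm 1 / Arm 5 rate | Table 7 | null variance | non-null |
|---|---|---|---|
| 25% / 10% | 0.686 | 0.699 | 0.747 |
| 40% / 25% | 0.528 | 0.546 | 0.572 |
| 45% / 25% | 0.739 | 0.748 | 0.771 |
| 50% / 25% | 0.889 | 0.888 | 0.902 |
| 25% / 25% | 0.045 | 0.049 | 0.060 |

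Table 7 is closer to the null variance. It shows null rejection for Arm 1 vs 5 only at rates of 25–35%.

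**One table worked through: 3/90 vs 0/45.** d = 0.0333.
- Non-null SE = √(0.0333×0.9667/90) = 0.0189, z = 1.76, p = 0.039.
- Null: p̄ = 3/135 = 0.0222, SE = √(0.0222×0.9778×(1/90+1/45)) = 0.0269, z = 1.24, p = 0.108.
- Fisher: (90×89×88)/(135×134×133) = 0.29.

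At a 5% rate, 0/45 has probability 0.95^45 = 0.099.

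**Type I error, 90 vs 45.**

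| common rate | 1% | 2% | 3% | 4% | 5% | 10% |
|---|---|---|---|---|---|---|
| nominal 0.05, non-null | 0.039 | 0.108 | 0.131 | 0.121 | 0.104 | 0.082 |
| nominal 0.05, null | 0.000 | 0.004 | 0.014 | 0.025 | 0.033 | 0.041 |
| nominal 0.025, non-null | 0.008 | 0.043 | 0.073 | 0.081 | 0.075 | 0.048 |
| nominal 0.025, null | 0.000 | 0.000 | 0.001 | 0.005 | 0.009 | 0.018 |

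A four-stratum simulation (200,000 runs) agrees: at nominal 0.05 and rates of 3% and 5%, the Sato standard error gives 0.132 and 0.103, and CMH gives 0.014 and 0.033.

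**Equal allocation.** With n1 = n2 = n, the null variance exceeds the non-null one only by (p̂1−p̂2)²/(2n), so the two tests nearly coincide. At nominal 0.05 the exact maximum is 0.059 for 45:45 (Arm 5 vs 6) and 0.062 for 90:90 (Arm 1 vs 3).

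**Min test at 0.025, non-null standard error, Arms 1 and 5 equal.**
- Arm 3 at 0%: 0.073–0.081 for rates of 3–5% in Arms 1 and 5.
- Arm 3 at 1%: 0.032–0.042 for the same rates.
- Arm 3 at 2%: 0.014–0.025.
- All three arms equal at 2–5%: 0.005–0.007.

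The primary min test at 0.05 behaves alike: up to 0.131 with Arm 3 at 0%, but 0.012–0.022 with all arms equal at 2–5%.

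**Gate.** In a simulation with Arms 2–4 at about 25% and Arms 1 and 6 at 5%, the MCP step included, the Arm 1 vs 6 error was 0.106 (non-null) against 0.034 (null).

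**The case against.** The strongest reply is that the SAP names the 1959 test and prescribes no non-null variance. A reader might infer that the SAP specifies an invalid standard error. It does not: no variance is stated, and the pooling method is left to a cited source. The choice is open, and it changes the error severalfold. But the rule asks for an estimate of the difference and its standard error, and its natural implementation is the non-null form.

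Three further readings go too far.
- That all four pairwise tests are inflated: Arm 5 vs 6 and Arm 1 vs 3 have equal allocation and stay near nominal.
- That the functional-cure regimen claim runs at 0.075: that is the Arm 1 vs 5 component. Both components must succeed, so the claim reaches that level only with Arm 3 essentially at zero. Protocol 2.2.1 points the other way, reporting marked HBsAg decline with JNJ-3989 and none of relevance so far with JNJ-6379.
- That the problem worsens as rates approach zero: at 1% the error is 0.039. Protocol Table 8 puts mean seroclearance on NA alone below 1%, and the main functional-cure comparisons with control use a fixed 5% benchmark, not the MH test.

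It is also fair that the Arm 1 vs 6 figure needs the MCP gate open. Under the global null the gate limits the error to its own level. The exposed case is that the JNJ-3989 doses work and Arm 1 does not, which is unlikely because Arm 1 contains the same 100 mg dose as Arm 3; strong error control must still cover it. Finally, the Table 7 comparison is only indicative. The planning test is described without stratification, and two null-variance values miss the table by about three simulation standard errors (0.018 against 0.005, and 0.013 against 0.005, at 10,000 runs).

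**Conclusion.** The point stands for the two 2:1 comparisons. Implemented with the usual MH risk-difference standard error, the stated rule does not deliver the error control claimed in SAP 5.1.1. For Arm 1 vs 6 (gate open) and Arm 1 vs 5, the one-sided error is about 0.10–0.13 at common rates of 2–5%, roughly double the nominal 0.05 or more. The Arm 1 vs 5 component at 0.025 runs at about 0.04–0.08. The SAP guards against sparse responders in the MCP step (Firth's method, and a variance calibrated by simulation in 5.3.2.1.1.1), but shows no such check for the pairwise tests.

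These figures assume equal true rates in the two arms, the planned sample sizes and complete data. The variance and finite degrees of freedom added by imputation were not modelled. The stratified results also rest on the assumed split of the suppressed participants, although the unstratified exact results agree with them.

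**What to change.** In SAP 5.2.2.1.4 and 5.3.2.1.4, and in the supplementary analysis in 5.3.4.1, state that p-values come from the stratified CMH statistic with its null variance. Compute the signed z in each imputed dataset and pool with standard error 1, as 5.2.2.1.4 already does for the MCP step. Keep the MH difference and its standard error for the point estimate and 90% CI only. Add a short table of Type I error at rates of 1–5% for the 90:45 comparisons.

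The cost is a change of wording and a small change in programming. Ungated power for Arm 1 vs 6 at 25% vs 5% falls from 0.964 to 0.946. The test becomes conservative at very low rates (0.014 at 3% for nominal 0.05; 0.001 for nominal 0.025), which should be accepted openly. SAP Amendment 2 refers to past interim analyses, and all of these follow the primary analysis. If the pairwise tests have already been run, the report should therefore state which standard error was used and show the null-variance p-values beside the results.
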